#### Pharmacodynamic Parameters

- Serum concentrations of keratan sulfate at every time point.

#### Lower back or leg pain

Lower back and leg pain assessed using an 11-point numerical rating scale. Visit value and change from baseline average daily, worst daily and current lower back pain or leg pain (numerical pain scale) at 6 and 13 weeks will be summarized by cohort. Visit value and change from baseline for other visits also summarized in a separate table. Listing will be provided for lower back and leg pain data [1]. Line graphs of baseline and post-baseline values for each pain categories will be graphically displayed for each subject by cohort.

#### Use of rescue medication or surgical intervention

The number of subjects used rescue medications and list of rescue medication will be summarized by cohort and it will be listed. Summarization includes additional pain medication (and amounts) added to the subject's baseline pain regimen within the first 13 weeks post-dose, an epidural injection, a selective nerve root block, or a facet block after receiving study drug and surgical intervention for lumbar disc herniation.

### **Spinal flexion and tension**

Spinal flexion and tension measured using the straight-leg raising or femoral stretch test at baseline, on day 1 pre-dose, at 24 hours post-dose and at all post-dose visits. Visit value and change from baseline (i.e. percentage change from baseline) in spinal flexion and tension signs (straight-leg raising or femoral stretch test) on the affected side at 6 and 13 weeks will be summarized by cohort. Rest of the time point details will be summarized same as mentioned above as a separate table. Listing will be provided for the spinal flexion and tension data.

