	
Pharmacokinetic analysis:
 
Serum concentrations of KTP-001 will be determined [REDACTED]
 
A noncompartmental analysis will include determination of the following parameters using WinNonlin® Professional Network Edition, version 5.2 or higher, Pharsight Corp, Palo Alto, CA:
 
• Maximum observed serum concentration (C_{max})• Time to C_{max} (t_{max})• Area under the concentration-time curve from time zero to time (t) (AUC_t). 
Exploratory efficacy endpoints and analysis:
 
The following efficacy endpoints will be analyzed and presented using descriptive statistics (n, mean, median, minimum, maximum, SD, percentage of analysis population, and CI):
 
• Change from baseline in lower back pain and leg pain (numerical pain scale) at 6 and 13 weeks• Number of subjects requiring 1) additional pain medication (and amounts) added to the subject's baseline pain regimen within the first 13 weeks post-dose, 2) an epidural injection, a selective nerve root block, or a facet block after receiving study drug, 3) surgical intervention for lumbar disc herniation• Change from baseline in spinal flexion and tension signs (straight-leg

	
raising or femoral stretch test) on the affected side at 6 and 13 weeks
 
• Change from baseline in ODI at 6 and 13 weeks• Change from baseline in SF-12 at 6 and 13 weeks• Change from baseline in the PGI-C at 6 and 13 weeks. 
Exploratory PD analysis: The following exploratory PD endpoint will be analyzed and presented using descriptive statistics (n, mean, median, minimum, maximum, SD, percentage of analysis population, and CI):
 
• Change from baseline in serum concentrations of keratan sulfate at every time point.
--	---------------------------------------------------------------------------------------------------------------------------------------------------------------------------------------------------------------------------------------------------------------------------------------------------------------------------------------------------------------------------------------------------------------------------------------------------------------------------------------------------------------------------------------------------------------------------------------------------------------------------------------------------------------------------------

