8 EFFICACY ASSESSMENTS

The following efficacy measures are all exploratory in nature and all analyses will be presented using descriptive statistics. For all measures, the baseline value is defined as the last assessment result collected prior to the first dose of study medication. Unless otherwise noted, the endpoint for all efficacy measures will be changes from baseline at 6 and 13 weeks post-dose.

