8.3 Spinal Flexion and Tension

Spinal flexion and tension will be measured using the straight-leg raising or femoral stretch test at baseline, on Day 1 pre-dose, at 24 hours post-dose, and at all post-dose visits. Details on administering the straight-leg or femoral stretch test are provided in [Appendix D](#).

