#### **6.7.1.6 Neurologic assessments**

Neurological examination results and change from baseline will be summarized for all scheduled time points by cohort. Information includes: deep tendon reflexes (patellar [or knee], Achilles [or ankle] as normal, decreased, absent, increased or clonus and Babinski's Sign as present, plantar flexion or no response); muscle strength (hip flexion, knee flexion, knee extension, ankle dorsiflexion/long toe extension, ankle plantar flexion as normal, decreased to resistance, against gravity only/no resistance, or no movement); sensory exam to pin-prick (anterior knee, medial malleolus, dorsum of the foot, anterior toes 1-3 and anterior toes 4-5 and lateral malleolus as normal, decreased/abnormal or absent) and overall clinical impression since baseline (as improved, remain unchanged or worsened). Positive straight-leg raising or femoral stretch test will also be summarized. A data listing of neurological evaluations will be provided.

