### **6.7.2 Analysis of Exploratory Efficacy Endpoints**

Exploratory efficacy endpoints analyses will be performed on the full analysis set and per protocol set and all analyses will be presented using descriptive statistics as mentioned in the [section 4](#). For all measures other than the daily pain, the baseline value is defined as the last assessment result collected prior to the first dose of study medication. For daily pain assessments, the baseline value is defined as the average of the results of 5 consecutive days prior to the first dose of study medication.

The following are the primary exploratory efficacy endpoints:

- Change from baseline in lower back pain or leg pain (numerical pain scale for each sub categories as mentioned below) at 6 and 13 weeks

- Leg average daily pain
- Leg worst daily pain
- Low back average daily pain
- Low back worst daily pain
- Current leg pain
- Current low back pain
- Number of subjects requiring:
  - Additional pain medication (and amounts) added to the subject's baseline pain regimen within the first 13 weeks post-dose
  - An epidural injection, a selective nerve root block, or a facet block after receiving study drug,
  - Surgical intervention for lumbar disc herniation
- Change from baseline in spinal flexion and tension signs (straight-leg raising or femoral stretch test) on the affected side at 6 and 13 weeks
- Change from baseline in ODI at 6 and 13 weeks
- Change from baseline in SF-12 at 6 and 13 weeks
- Change from baseline in the PGI-C at 6 and 13 weeks

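### SAP 6.7.2 defines change in the straight-leg-raising or femoral stretch test as percentage change, against the protocol and its own endpoint list, and the measure suits neither a sign nor an angle

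*SAP*

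**What the plan says.** The protocol synopsis lists as an exploratory efficacy endpoint "Change from baseline in spinal flexion and tension signs" on the affected side at 6 and 13 weeks. Protocol Section 8 sets the general rule: "Unless otherwise noted, the endpoint for all efficacy measures will be changes from baseline at 6 and 13 weeks post-dose". Section 8.3 names the test and the visits ("Spinal flexion and tension will be measured using the straight-leg raising or femoral stretch test at baseline") and refers to Appendix D for its administration. It notes no exception to the general rule and gives no unit.

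The endpoint list in SAP 6.7.2 keeps the protocol wording: "Change from baseline in spinal flexion and tension signs (straight-leg raising or femoral stretch test) on the affected side at 6 and 13 weeks". Later in 6.7.2, the paragraph on spinal flexion and tension specifies something else: "Visit value and change from baseline (i.e. percentage change from baseline) in spinal flexion and tension signs". The words that make the difference are "i.e. percentage change from baseline". The paragraphs on pain, ODI, SF-12 and PGI-C contain no such parenthesis.

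On the safety side, SAP 6.7.1.6 says: "Positive straight-leg raising or femoral stretch test will also be summarized". SAP 9.0 lists two changes from the protocol, the removal of the PK parameter analysis and of the rescue-medication counts. It does not mention this one.

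**The concern.** The parenthesis opens with an i.e., so it defines the change to be tabulated; it does not add a second summary beside it. A programmer who follows that paragraph would produce a different table from one who follows the endpoint list in the same section.

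The chosen measure is also a poor fit for the data. Where the documents show the form of the result, it is a sign that is positive or not: inclusion criterion 2, the safety endpoints in the protocol synopsis, and SAP 6.7.1 and 6.7.1.6. Dividing a change in a sign by its baseline has no clinical meaning. If an angle is recorded instead, the percentage depends on where each subject started as well as on how far the subject moved.

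At stake is whether this change summary, read cohort by cohort with 6 subjects each, can be interpreted.

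**Working it through.** The plan gives no figure for this endpoint, so there is nothing to reproduce. The formula implied by the SAP paragraph is 100 × (follow-up − baseline) / baseline. Baseline is the last result before dosing (SAP 4.0), and cohorts have 6 subjects (protocol synopsis). The documents give neither a coding nor any angle, so both are assumed below.

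**If a sign is recorded**

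| Coding (negative, positive) | Positive to negative | Positive to positive | Negative to positive | Negative to negative |
|---|---|---|---|---|
| 0, 1 | (0 − 1)/1 = −100% | 0% | undefined (divide by 0) | undefined (divide by 0) |
| 1, 2 | (1 − 2)/2 = −50% | 0% | (2 − 1)/1 = +100% | 0% |
| 2, 1 | (2 − 1)/1 = +100% | 0% | (1 − 2)/2 = −50% | 0% |

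One clinical event, a positive test turning negative, scores −100%, −50% or +100% depending on the code list. A count of positives or a shift table does not depend on the coding.

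**If an angle is recorded**

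A 20-degree gain gives 100 × 20 / baseline:

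| Baseline (degrees, assumed) | 5 | 10 | 20 | 30 | 45 | 70 |
|---|---|---|---|---|---|---|
| Percentage change | +400% | +200% | +100% | +67% | +44% | +29% |

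Next, take a cohort of 6 in which every subject gains exactly 20 degrees, and change only one baseline. The interval is mean ± t × SD/√6 with 5 degrees of freedom.

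| Baselines (assumed) | Mean | SD | 95% CI | Median |
|---|---|---|---|---|
| 30, 35, 40, 45, 50, 60 | 48.6% | 12.0 | 36.0 to 61.2 | 47.2% |
| 10, 35, 40, 45, 50, 60 | 70.8% | 63.8 | 3.9 to 137.8 | 47.2% |
| 5, 35, 40, 45, 50, 60 | 104.2% | 145.2 | −48.2 to 256.5 | 47.2% |

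The absolute change is 20 degrees for every subject in all three rows. The mean and interval move with one baseline; the median does not.

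To see how far this matters when gains vary, 100,000 cohorts of 6 were simulated with uniform baselines and gains of mean 15 and SD 10 degrees (all assumed). The coefficient of variation of the cohort mean was 0.27 for absolute change. For percentage change it was 0.29 with baselines of 30 to 60 degrees, 0.33 with 20 to 70, 0.40 with 10 to 70 and 0.50 with 5 to 70. The penalty is therefore negligible unless some baselines are low.

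**The case against.** The strongest reply is that the content of Appendix D is not visible, so neither the sign nor the angle case is shown to apply. That stands, and the conclusions here are conditional on the data type.

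A second reply is that the parenthesis may mean the change in the percentage of subjects who are positive. That would fit the word signs and the SAP 4.0 rule that categorical data are summarised by n and percentage. It is a sensible reading, but the SAP does not state it, and an unstated choice between two tables is itself a reason to correct the wording.

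Third, SAP 1.0 presents the SAP as giving further detail and promises documentation only of major deviations, and the protocol does not say that change must be absolute. Whether an entry in 9.0 was strictly required is therefore arguable. The disagreement between the two parts of SAP 6.7.2 does not depend on that.

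Fourth, much of what is needed is already planned. Visit values and a listing come with the same paragraph, SAP 4.0 adds median, minimum and maximum, and 6.7.1.6 summarises positive tests and neurologic change from baseline at all scheduled visits. This limits the harm, because an outlier would be visible and absolute change could be recovered. It leaves the stated efficacy change summary as it is.

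**Conclusion.** The point holds as a conflict in the wording together with a poorly chosen measure, and it is minor. Followed as written, the rule gives a degenerate and coding-dependent value for a sign, and a baseline-dependent value for an angle. The consequence stops at one change summary in an exploratory, descriptive analysis.

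A reader might infer three stronger things that the documents do not support:

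- **That the measure is simply undefined for a sign.** This is strict only when baseline is coded 0. Inclusion criterion 2 requires a documented positive test, so most baselines should be positive, although a negative test before dosing on Day 1 remains possible.
- **That it is unstable for an angle.** This depends on baselines that the documents do not give. At 30 to 60 degrees the coefficient of variation is 0.29 against 0.27; marked instability needs some baselines near 5 to 10 degrees.
- **That percentage change is what prevents this endpoint from showing a dose effect.** No hypothesis test is planned, and 6 subjects per cohort could not show a dose effect reliably on absolute change either.

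**What to change.** In the Spinal flexion and tension paragraph of SAP 6.7.2, delete the parenthesis and state what is recorded.

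- If it is a sign, report n (%) positive at each visit and a shift table from baseline to Week 6 and to Week 13, on the affected side, by cohort.
- If it is an angle, report absolute change in degrees, with the summary statistics already listed in SAP 4.0.
- If percentage change is kept as a supplement, say so and record it in SAP 9.0.

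The cost is SAP wording and the matching table shell. No new data and no protocol amendment are needed.

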### **Functional ability**

The Oswestry disability index (ODI) is a patient self-scored questionnaire and a validated tool to measure how functional level is restricted by disability, and can also be used to determine improvement in functional levels as a result of treatment. The ODI will be administered at baseline, on day 1 pre-dose, at 24 hours post-dose, and at all post-dose visits. The improvement or lack of improvement in functional level is determined as a change from baseline in the score. Visit value and change from baseline in ODI at 6 and 13 weeks will be summarized by cohort. Rest of the time point details will be also summarized. Listing will be provided.

Score is calculated as patient score/total possible score x 100 = %. Scores will be grouped into levels of disabilities of 0% - 20% = minimal disability, 20% - 40% = moderate disability, 40% - 60% = severe disability, 60% - 80% = crippled, 80% - 100% = bed bound and it will also summarize.

### **Quality of life**

Quality of life evaluated using the SF-12 form (version 2.0). 8 domains scores will be summarized for change from baseline in the SF-12 at 6 and 13 weeks descriptive by cohort. Quality of life results will be displayed in the subject data listings. The SF-12 will be administered at baseline, on day 1 pre-dose, at 24 hours post- dose, and at all post-dose visits. Rest of the time point details will also be summarized.

### **Global impression of change or improvement**

Global impression of improvement as measured by the patient global impression of change (PGI-C) is a single question survey that will be administered at baseline, on day 1 pre-dose, at 24 hours post-dose and at all post-dose visits. Visit value and change from baseline in PGI-C score at 6 and 13 weeks will be summarized by cohort. Visit value and change from baseline for other visits also summarized in a separate table same as mentioned above. Listing will be provided for PGI-C score.

### **Magnetic Resonance Imaging Assessment**

Magnetic resonance evaluation on the modification/shrinkage of the treated herniated disc size, the improvement of the stenosis of spinal canal, and the reduction of associated lateral neural foramen compression will be performed at Week 13, and at Months 6, 12, 18, and 24 (or early termination). Visit value in treated herniated disc size, the improvement of the stenosis of spinal canal, and the reduction of associated lateral neural foramen compression for each visit

will be summarized by cohort and will be presented using descriptive statistics as mentioned in the [section 4](#).

The correlation between imaging findings and symptoms (e.g., average daily, worst daily and current lower back pain or leg pain values and ODI score) will be conducted after database lock as part of the report analysis for each visit by cohorts. Spearman rank correlation coefficient and p-value will be presented. Additionally listing will also be provided.

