8.1 Lower Back or Leg Pain

Lower back and leg pain will be assessed using an 11-point numerical rating scale in response to the questions provided in [Appendix C](#) at screening, for 5 consecutive days prior to Day 1, pre-dose, at 2, 4, 6, and 24 hours post-dose, and then daily until the Week 13 visit. A numerical rating scale is considered to be a valid and reliable means of measuring pain in subjects with chronic pain conditions ^[14].

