12 STATISTICAL CONSIDERATIONS

12.1 General Considerations

All statistical analyses will be conducted using SAS software, version 9.1.3 or higher (SAS® Institute, Cary, NC). Additional analyses of study endpoints will be detailed in the statistical analysis plan.

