12.2 Sample Size Calculation

The sample size of 24 subjects in 4 cohorts is considered appropriate for a study of this type and was determined by practical considerations. No formal sample size calculation was made as no formal hypothesis testing will be performed.

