12.7 Efficacy Analysis

All efficacy analyses are exploratory in nature and will be presented using descriptive statistics only (n, mean, median, minimum, maximum, SD, percentage of analysis population, and confidence intervals). Post-dose change from baseline in lower back or leg pain will be tabulated by dose level in a table summary.

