#### 4.0 STATISTICAL CONSIDERATIONS

Statistical analyses will be performed using SAS software, version 9.3 or higher. The safety population will be used as the analysis population for the primary endpoints and all safety end points. Full analysis set and per protocol set will be used as the analysis population for secondary and exploratory efficacy endpoints.

Continuous data will be summarized using n, mean, median, standard deviation (SD), minimum value, maximum value, 95% confidence interval (CI) and, if appropriate, number of missing values. Unless noted otherwise, summaries will be produced by visit (where applicable) and cohort. Summaries by visit will be based on nominal reporting. If more than one value is reported at a scheduled visit, the value collected closest to the intended visit date will be used. In the case of a tie, the latest version will be summarized.

Categorical data will be summarized using n, percentages. Percentages will be calculated based on the number of non-missing values. The number of missing values will be presented as a separate category with no percentage, if 1 or more patients are missing data for the summary. Otherwise, all categories will be presented (even if no patients are counted in the category). Counts of zero in any category will be presented with percentage as (0%).

Precision of summary statistics:

- Integer – Sample size (n, N) and number of missing responses (if displayed).
- One additional decimal place than reported/collected on the case report form (CRF) – mean, median, confidence interval.
- Two additional decimal places than reported/collected on the CRF – standard deviation.
- Same number of decimal places as reported/collected on the CRF – minimum, maximum.
- Percentages – one decimal place.

All data will be presented on listings in order of dosing cohort, patient, assessment date/time and assessment (in order collected on eCRF, unless specified otherwise). For display purposes, cohort labels will be ordered from smallest to largest. Dates will be presented in the format DDMMYY. Times will be displayed in 24-hour clock format. Numbering of tables, figures and listings will follow ICH E3 guidelines.

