## **9.0 CHANGES FROM ANALYSIS METHODS PLANNED IN THE PROTOCOL**

The planned protocol analysis of PK parameters and summary on counting the rescue medications were removed.

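### Imaging-symptom Spearman correlations are planned only within cohorts of 6, with p-values and no CI: add a pooled, cohort-adjusted estimate, and reconcile the texts on symptom data at Months 18 and 24

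*SAP*

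**What the plan says.** Protocol 8.8 plans a correlation between imaging findings and symptoms after database lock and does not confine it to cohorts. The SAP (6.7.2, Magnetic Resonance Imaging Assessment) adds that confinement: the correlation is done "as part of the report analysis for each visit by cohorts", and "Spearman rank correlation coefficient and p-value will be presented". The imaging findings are herniated disc size, canal stenosis and foraminal compression; the symptoms are average daily, worst daily and current pain, and ODI. No pooled estimate, p-value method or CI for the coefficient is given. SAP 4.0 does include a "95% confidence interval (CI) and, if appropriate, number of missing values" in its summaries of continuous data.

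Protocol 12.7 says efficacy analyses "will be presented using descriptive statistics only" and counts confidence intervals among them. Protocol 12.2 says "No formal sample size calculation was made as no formal hypothesis testing will be performed". Protocol 12.1 adds that "Additional analyses of study endpoints will be detailed in the statistical analysis plan".

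On timing, post-dose MRI is at Week 13 and Months 6, 12, 18 and 24. Diary pain is rated before dosing and during confinement, "and then daily until the Week 13 visit". The synopsis names Months 18 and 24 for pain. Protocol 8.3 to 8.6 and the matching parts of SAP 6.7.2 put spinal flexion/tension, ODI, SF-12 and PGI-C at every post-dose visit. Protocol 11.11 (Month 18) and 11.12 (Month 24) list none of these five measures, and 11.14 applies the 11.12 list to early termination after Week 13. The lists for Months 6, 9 and 12 contain all five.

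**The concern.** A rank correlation on six pairs is too imprecise to read even as description. Four such coefficients side by side, in order of dose, invite the reader to see a dose pattern in what may be chance differences in sign. The p-value does not help: at this size it depends on a method the SAP does not name, and it says less than an interval would. The same data, pooled, would support a usable estimate.

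The timing conflict bears on the same analysis. It is planned for each visit, but on the Section 11 text the Month 18 and Month 24 MRIs have no pain or ODI score to pair with, and average and worst daily pain can be paired only with the Week 13 MRI.

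**Working it through.** **Inputs.** 4 cohorts of 6, so 4 × 6 = 24 (protocol synopsis). The documents give no expected correlation, alpha or dropout rate. Estimates of 0.3, 0.5 and 0.7, and 20 or 16 subjects with data, are assumptions. There is no planned figure for precision to reproduce.

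**Interval.** z = atanh(r); SE = √(1.06/(n − 3 − k)); limits tanh(z ± 1.96 SE). Here k = 0 within a cohort and k = 3 for the pooled partial coefficient (three cohort terms). For r = 0.5, z = 0.549:

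- One cohort, n = 6: SE = √(1.06/3) = 0.594, giving -0.55 to 0.94.
- Pooled, n = 24: SE = √(1.06/18) = 0.243, giving 0.07 to 0.77.
- Pooled, n = 20: SE = √(1.06/14) = 0.275, giving 0.01 to 0.80.

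| Estimate | One cohort, n = 6 | Pooled and adjusted, n = 24 |
|---|---|---|
| 0.3 | -0.69 to 0.90 | -0.16 to 0.66 |
| 0.5 | -0.55 to 0.94 | 0.07 to 0.77 |
| 0.7 | -0.29 to 0.97 | 0.37 to 0.87 |

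With the alternative variance (1 + r²/2)/(n − 3 − k), the intervals at r = 0.5 are -0.57 to 0.94 (n = 6), 0.06 to 0.78 (n = 24) and -0.01 to 0.80 (n = 20). At n = 16 the two variances give -0.09 to 0.83 and -0.11 to 0.84.

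**Sign errors.** In simulation with a true correlation of 0.5 (bivariate normal), one cohort's estimate has the wrong sign about 15% of the time. With the simulated 0.146, at least one of four cohorts does so with probability 1 − (1 − 0.146)⁴ = 0.47. For the pooled estimate at n = 24 the figure is about 1.4%.

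**Why adjust for cohort.** With no within-cohort correlation and assumed cohort shifts of 0, 0.5, 1 and 1.5 SD in both variables, the unadjusted pooled coefficient averaged 0.23 and the adjusted one -0.01. Simulated coverage of the adjusted 95% CI was 94.4% to 95.9%, with continuous data and with integer pain scores.

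**P-value.** Over all 720 orderings of six untied pairs, |rho| of at least 0.829 has probability 42/720 = 0.058. By the t-approximation, t = 0.829 × √(4/(1 − 0.829²)) ≈ 2.96 on 4 df, p = 0.042. The two methods fall on opposite sides of 0.05.

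**Timing, side by side.**

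| Measure | Text that includes Months 18 and 24 | Protocol 11.11 and 11.12 |
|---|---|---|
| Pain | Synopsis, by name | Not listed |
| Spinal flexion/tension | Protocol 8.3, SAP 6.7.2 | Not listed, but both leg tests are in the neurologic examination (9.7), which is listed |
| ODI, SF-12, PGI-C | Protocol 8.4 to 8.6, SAP 6.7.2 | Not listed |
| MRI | Protocol 8.8 and 9.6, SAP 6.7.2 | Listed |

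The schedule tables are damaged in the text copy. In both, however, the pain row carries three footnote marks for clinic-visit-only assessment, which matches Months 6, 9 and 12 and so agrees with the visit lists.

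**The case against.** The analysis is exploratory, by-cohort presentation is the SAP's general rule (4.0 and 6.7), and a listing is planned, so anyone could pool later. That stands, and it limits the weight of the point. It does not make the planned coefficients readable.

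The gain from pooling is modest. At 0.3 the pooled interval still includes zero, and at 0.5 with 20 subjects it starts at about zero. Fewer than 24 is plausible, because lumbar surgery means discontinuation and missing values are not imputed. Two of the three imaging findings are qualitative, so ties are expected: with an assumed skewed three-level grade, an underlying 0.5 gave a mean pooled estimate of about 0.34, with an interval at n = 24 of about -0.12 to 0.68. Ties also mean that the p-value example above is only illustrative. Adjustment has a price too: across doses from 5 to 150 µg, imaging and symptoms may move together because of dose, and the adjusted coefficient removes that. These objections all stand and belong in the SAP as stated limits.

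A reader might infer that the p-values breach the protocol. The documents do not support this. A p-value beside an exploratory coefficient is not formal hypothesis testing, and protocol 12.1 leaves room for added analyses in the SAP. What remains is missing detail: no method is named, and SAP 9.0 records only that "The planned protocol analysis of PK parameters and summary on counting the rescue medications were removed".

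A reader might also infer that sites cannot tell what to collect at Months 18 and 24, or that a large block of data will be lost. That is too strong. The visit lists, and apparently the schedules for pain, consistently stop at Month 12. For ODI, SF-12 and PGI-C the synopsis itself names only Weeks 6 and 13 or early termination. A count such as 5 measures × 2 visits × 24 subjects = 240 would assume full retention and include assessments that Section 11 does not list.

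**Conclusion.** The point holds as a low-cost improvement to an exploratory analysis. Each planned by-cohort coefficient is nearly uninformative; a pooled, cohort-adjusted coefficient is clearly more precise, though still wide. The size depends on the assumed correlation, on how many of the 24 subjects have data, on the approximate interval formula, and on a roughly common within-cohort association. If the true correlation were 0.7 in two cohorts and 0 in the other two, the pooled estimate would average about 0.33.

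The timing conflict is real, but it is a matter of wording. If Section 11 governs, the correlations with pain and ODI cannot be computed at 2 of the 5 post-dose MRI visits, nor at early termination after Week 13. For spinal flexion/tension the conflict is softer, because the leg tests continue within the neurologic examination. Nothing here affects a primary safety conclusion or the 6- and 13-week endpoints.

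**What to change.** In SAP 6.7.2:

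- Add, per visit and imaging-symptom pair, one partial Spearman coefficient over all cohorts: rank both variables over all subjects, remove cohort means, correlate. Report n and a 95% CI; a bootstrap CI is reasonable for the qualitative findings.
- Keep the by-cohort coefficients and the listing as description, preferably without p-values. If p-values stay, name the method and record them in SAP 9.0.
- State the two limits: a similar within-cohort association is assumed across doses, and between-dose co-movement is removed. The by-cohort coefficients let the reader look at the first.
- Restrict the correlations to visits where both variables are collected, and use average and worst daily pain at Week 13 only.

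In both documents, reconcile the synopsis, protocol 8.3 to 8.6 and SAP 6.7.2 with protocol 11.11, 11.12 and 11.14 for all five measures. Either the visit lists carry them, or the text says that these data end at Month 12 and that the leg tests continue within the neurologic examination.

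The correlation change costs some SAP wording and one table. The reconciliation is text only if the Month 18 and 24 visits are over or the data are to end at Month 12; otherwise it means short assessments at visits already scheduled. The SAP is dated 03May2018, and the documents do not say which case applies.
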